#### Method

#### Design

A pilot randomised controlled trial with **two parallel comparator groups**; the ReFresh online fatigue management program versus a wait list group who will receive treatment as usual, and then access the ReFresh online course at week 14 to ensure all end point data is gathered. We will recommend participants access one **module per week** i.e. six modules over six weeks, and undertake at **least three 30 minute sessions of exercise per week**. The primary outcome will be fatigue at 12 weeks. All measures will be unblinded as it is impossible to blind participants as to whether they have accessed the web site or not.

This pilot study will check study processes (e.g., recruitment, randomisation, treatment, follow-up assessments) all run smoothly, and determine the acceptability and practicality of the ReFresh intervention. It will also appraise the feasibility and sensitivity of two fatigue measures in order to decide which measure will be the primary outcome measure in the fully powered RCT this pilot study will inform. The fatigue measures are the Parkinson's Fatigue Scale (PFS) (Baghoori 2017) and the Modified Fatigue Impact Scale (MFIS) (Fisk et al., 1994). These will be measured at baseline and 12 weeks. Once the primary measure is selected it will inform the number of participants required for a fully powered RCT.

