## Aims

- To determine the size and variance of the difference in change in fatigue between
  the ReFresh group versus the waitlist group at 12 weeks. This will be used calculate
  the number of participants needed to fully power a randomised controlled trial to
  determine efficacy.
- To assess the feasibility, acceptability, and safety, of the ReFresh online fatigue management intervention.
- To assess the feasibility and acceptability of the design of the RCT protocol. In particular to determine which measure of fatigue to use as the primary outcome measure in the planned fully powered RCT.

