#### Randomisation and stratification

Upon completion of baseline data, participants will undergo randomisation to either the intervention arm (fatigue management) or the control arm (waitlist) utilizing the Sealed Envelope website. Sealed Envelope offers a robust online software application for randomising patients into clinical trials and capturing case report form data (EDC and ePRO).

The Simple randomisation service provided by Sealed Envelope will be employed for this trial. This uses a pseudo-randomisation number generator, and will allocate participants in a 1:1 ratio to ReFresh or wait list. To ensure a reasonably even distribution of patients in the 2 arms throughout the course of the trial, patients will be allocated in randomly permuted blocks of 4 and 6 (Sealed Envelope Ltd. 2022).

For the trial, a unique password will be assigned. Authorized personnel with the password will have the capability to conduct new randomisations. The results will be promptly displayed on-screen and emailed to both the trial administrator and the assigned individual overseeing the randomisation process, ensuring transparency and accountability.

Upon allocation participants will be sent an email informing them of their allocation. If allocated to the ReFresh group they will be sent the link to the ReFresh online program https://www.uea.ac.uk/web/groups-and-centres/projects/fatigue-management-in-parkinson-s/refresh-study-getting-started. If they are allocated to the waitlist group they will be told they will be contacted again in 12 weeks to complete the end point survey, and then at 16 weeks with the link to the ReFresh program (to ensure no contamination of the control group).

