#### Outcomes

Assessments will take place at baseline and 12 weeks after randomisation.

We anticipate that the ReFresh program will improve fatigue. In this pilot RCT we will use two measures of fatigue; the Parkinson's Fatigue Scale (PFS) (Baghoori 2017) and the Modified Fatigue Impact Scale (MFIS) (Fisk et al., 1994). These two measures assess related but not identical concepts. The PFS focusses on the experience of fatigue with some items that examine its impact on activities. Whereas the MFIS focusses far more on the impact having fatigue has on physical, social, and cognitive activities. We are unsure whether the ReFresh program will just impact on the sense of fatigue, or whether it will impact on participant's activity levels, so we will use both measures to determine which is most sensitive to any changes caused by the ReFresh program. MFIS is commonly used in fatigue research, and so these results could be more easily compared against other fatigue management protocols. The MFIS has excellent psychometric properties in multiple sclerosis populations; with internal consistency, Cronbach  $\alpha$  of 0.92 (Kos 2005), and a testretest reliability intraclass correlation coefficient (ICC) of 0.91, (Kos 2003). Although MFIS was not developed for Parkinson's it has been validated with this patient population; where it has high internal consistency, Chronbachs  $\alpha$ =0.96 (Schiehser 2012). However, the PFS was specifically developed and validated in people with Parkinson's (Baghoori 2017) and may therefore be more sensitive to disease specific factors. It is also a robust measure with a high internal consistency (Chronbach's  $\alpha$ =0.98) and good test-retest reliability Spearman R mean 0.63±0.06). The data from this pilot will allow us to refine the design of the planned

fully powered RCT to ensure its primary outcome uses the measure most likely to be sensitive to the changes possible from the ReFresh program.

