#### *Resource utilisation*

We will use a self-reported health and social services resource utilisation survey with a 3-month recall period (collected at the 12-week follow-up point only). This will include tracking appointments with GPs, consultants, OTs, PTs, if there is a change in their medications, or if they access any complementary therapies etc during period of study.

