#### **Efficacy Analyses**

As this is a pilot RCT an accurate assessment of the efficacy of the intervention cannot be determined as the study is insufficiently powered. However, we will analyse the primary outcome measure at 12 weeks using the parametric student-t test for comparing mean change between the two intervention groups.

Intention to Treat (ITT) analyses will be performed for all outcomes and will comprise of all patients who had been randomised. For the intervention group, this was irrespective of their compliance with the ReFresh program. The principle of ITT was adopted as it provides a pragmatic estimate of the benefit of a change in treatment policy compared to the potential benefit in patients who receive treatment exactly as planned. As the ReFresh program was planned for delivery over a six-week period, some participants may not have received all the planned sessions. As this is more likely to reflect usual practice, primary analyses of all outcomes were conducted according to the ITT principle. Per Protocol (PP) analyses was planned for participants who had not deviated from the ReFresh protocol in such a manner that the assessment of efficacy could be biased. This was defined as patients accessing at least four out of six ReFresh modules. Imputation of missing/incomplete data is planned to use last observation carried forward method for all outcome measures.

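### With fatigue assessed only at baseline and 12 weeks, last observation carried forward gives each participant without a 12-week score a change of exactly zero, distorting the estimates the first aim needs

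*Protocol*

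**What the plan says.** The rule is in the Protocol, Efficacy Analyses: "Imputation of missing/incomplete data is planned to use last observation carried forward method for all outcome measures". The same section says that the intention-to-treat analyses "will comprise of all patients who had been randomised" and that the primary outcome is analysed "using the parametric student-t test for comparing mean change between the two intervention groups".

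The schedule has two time points. Outcomes states: "Assessments will take place at baseline and 12 weeks after randomisation". Design says of the two fatigue scales, the MFIS and the PFS: "These will be measured at baseline and 12 weeks". Baseline cannot be the missing value, because Randomisation and stratification says: "Upon completion of baseline data, participants will undergo randomisation".

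The first item under Aims is "To determine the size and variance of the difference in change in fatigue between" the two groups at 12 weeks, to be used in calculating the size of a fully powered trial. Sample size justifies the 40 participants by the need to estimate parameters such as the standard deviation. Resource use is "collected at the 12-week follow-up point only". The protocol describes no other imputation method and no missing-data sensitivity analysis.

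**The concern.** Last observation carried forward presupposes some post-baseline observation to carry. Here there is none before week 12, so the method becomes baseline carried forward. In a change-score analysis of everyone randomised, a participant who does not return the 12-week survey is recorded as having had no change at all.

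The protocol itself says that the trial is too small to judge efficacy. The estimates passed on to the definitive trial therefore matter more than the t test. Artificial zeros enter both of the estimates named in the first aim. Unequal loss is also plausible: one arm works through a self-paced web programme, the other waits for access, and both know their allocation.

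**Working it through.** **The protocol's own figure.** Twenty per arm in two arms gives 2 × 20 = 40, as stated. The number rests on a rule of thumb. No dropout rate, SD, effect, alpha or power is given, so nothing further can be reproduced.

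**What the rule does (no assumptions needed).** For a participant with no 12-week score, the carried value is the baseline, so change = baseline − baseline = 0.

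**Bias in the mean.** Let a fraction q of an arm be missing, with true mean change m among those missing. The rule replaces m by 0, so the arm mean is wrong by −q·m. The error in the between-arm difference is −(q₁m₁ − q₀m₀). It is zero if nobody is missing, if m is zero in both arms, or if the two products happen to cancel.

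**Effect on the SD.** If missingness is independent of outcome, with true mean change μ and SD s:

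- mean after imputation = (1 − q)μ
- variance after imputation = (1 − q)s² + q(1 − q)μ²

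The variance is below s² whenever (1 − q)μ² < s², that is |μ| < s/√(1 − q). The limit is 1.05 s at q = 0.10 and 1.29 s at q = 0.40. The SD is therefore understated unless the mean change exceeds roughly one SD.

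**Illustration.** Assumed: s = 1, true mean change 0.5 in ReFresh (taken as the direction of benefit) and 0 in the wait list, and equal missingness q. Pooled variance is the average of the two arms.

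| q | Mean difference | Variance, ReFresh / wait list | Pooled variance | SD |
|---|---|---|---|---|
| 0.10 | 0.450 | 0.9225 / 0.900 | 0.911 | 0.95 |
| 0.25 | 0.375 | 0.797 / 0.750 | 0.773 | 0.88 |
| 0.40 | 0.300 | 0.660 / 0.600 | 0.630 | 0.79 |

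A simulation of 100,000 trials with 20 per arm agrees with the formulae. With true changes of −5 and 0, SD 10 and 20% missing per arm, it gave −3.99 and 9.05, against −4.00 and 9.06.

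**Consequence for the next trial (q = 0.25; 90% power and two-sided 5% assumed).**

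- Imputed SD with a fixed target difference: N ratio = 0.773, so the trial is 23% too small. True power = Φ(3.242 × 0.879 − 1.96) = 0.81.
- Imputed difference and imputed SD together: N ratio = 0.773 / 0.5625 = 1.375, so the trial is about 37% too large.

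**Unequal loss with no treatment effect.** Assume both arms change by 0.3 SD, with 35% missing in ReFresh and 10% in the wait list. The difference is 0.3 × 0.65 − 0.3 × 0.90 = −0.075 SD. Higher fatigue scores are worse, so this favours ReFresh if both arms worsen and counts against it if both improve.

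**Sampling error for scale.** With 20 per arm, the standard error of the difference is √(2/20) = 0.32 SD. A 95% interval for the SD on 38 degrees of freedom runs from about 0.82 to 1.29 times the estimate.

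**The case against.** The strongest reply is that this is a pilot with several aims, including feasibility, acceptability, safety and the choice of fatigue scale. The imputation rule sits in a section that disclaims efficacy, and at 20 per arm chance variation exceeds the bias. The false difference of 0.075 SD is about a quarter of one standard error. This bears on materiality and stands as context. It does not rescue the rule, because the bias is systematic and avoidable.

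A reader might infer more than the documents support in four ways.

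- *That everyone who drops out gets a zero.* The analysis ignores compliance, so someone who abandons the programme but returns the 12-week survey is analysed on real data. Only 12-week non-responders are zero-filled. How single missing items in a returned survey are handled is not stated.
- *That the dropout rate alone sets the bias.* The bias in the mean also depends on what the missing participants would have scored.
- *That the definitive trial will be too small, or too large, by a known amount.* The two sizing calculations point in opposite directions, and the protocol does not say which would be used. Nor does it say outright that the planning SD comes from imputed data. That is an inference, though a reasonable one, since no other analysis of change is described.
- *That the rule is at least conservative.* With unequal loss the error can go either way.

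The per-protocol analysis is no remedy: it selects on access to four of the six modules, not on return of the survey. The resource-use point is minor. There is nothing to carry forward there, so the rule cannot operate, but no bias follows.

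**Conclusion.** The point holds for participants with no 12-week score. That their change is set to exactly zero follows from the protocol's schedule and analysis rule alone. The consequences carry conditions: the SD is generally understated if anyone is missing, except where the mean change exceeds roughly one SD. The mean difference is biased unless non-responders' true mean change is zero in both arms, apart from chance cancellation.

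The figures are illustrations under assumed inputs: a shrinkage of 10% to 40% in the difference and an SD of 0.95 to 0.79 of its true value. They rest on a 0.5 SD effect confined to ReFresh and on equal missingness independent of outcome. They do not predict this trial's results. Because the protocol states the rule itself, this is a rule badly fixed and not a detail left to an analysis plan.

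**What to change.** Replace the imputation sentence under Efficacy Analyses.

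- **Primary analysis:** a baseline-adjusted ANCOVA of observed 12-week scores, each participant in the allocated arm, with the missing-at-random assumption stated. An equivalent likelihood-based model of baseline and 12-week scores would keep every randomised participant through the baseline value. If ANCOVA is chosen, amend the intention-to-treat wording, because non-responders then drop out of the analysed set.
- **Planning figures:** take the SD, the correlation between baseline and 12 weeks, and retention per arm from that un-imputed analysis.
- **Zero-change imputation:** keep it at most as a sensitivity analysis, labelled as baseline carried forward. Do not apply it to outcomes collected once, such as resource use.

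The cost is a few sentences, with no new data or participants. The downsides are small: reliance on missing-at-random, which the data cannot verify, and a slightly smaller analysed number under ANCOVA.

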#### **Primary Measures**

## **Fatigue**

- a. *Modified Fatigue Impact Scale (MFIS):* 21 items that assess the impact of fatigue on cognitive, physical, and psychosocial functioning. The total score ranges from 0 to 84, with higher scores indicating greater impact of fatigue (Fisk et al., 1994).
- b. *Parkinson's Fatigue Scale (PFS):* 16 items that mostly measure the experience of fatigue (Baghoori 2017). The total score ranges from 0 to 80, with higher scores indicating greater levels of fatigue.

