## Secondary measures

#### Parkinson's disease Questionnaire - 39:

Much research in Parkinson's has used the Parkinson's-specific quality of life scale PDQ-39 and have found it to be sensitive to a variety of treatments including therapeutic rehabilitation interventions (Fitzpatrick et al., 1997). It uses 39 items to assess eight dimensions of health: mobility, ADL, emotional wellbeing, stigma, social support, cognition, communication, and bodily discomfort.

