## Data security

Only members of the research group (members are listed at the start of this protocol) will have access to the data during the project.

Most of the assessments and consent will be recorded online using the Qualtric survey platform. However, to ensure accessibility for participants with disability access needs, participants will be offered hard copy survey and consent forms to be posted to them (including a postage paid return envelope). If participants take up this option, the information on these hard copies will be transcribed by SA into the Qualtrics surveys. All hard copy surveys and consent forms will be destroyed as soon as the data is transcribed to the Qualtrics platform.

The data will be downloaded from the Qualtrics platform to the secure UEA server, and the original data will be deleted from the Qualtrics platform by September 31st, 2025. The contact details will be kept only until everyone involved in the trial has been sent a link to the online fatigue management intervention i.e., 14 weeks after randomisation (September 31st, 2024, latest). After this we will destroy the contact details and keep the anonymised dataset of results.

Project data will be deleted from the UEA shared drive 10 years after the end of the project (i.e., 31st September 2035). Only anonymised data will be shared externally (e.g., in reports and publications).

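### Carry-forward is set for incomplete as well as missing data without stating item or total level; on totals, one skipped week-12 item would turn a response into no change

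*Protocol*

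**What the plan says.** The imputation rule is one sentence at the end of Efficacy Analyses: "Imputation of missing/incomplete data is planned to use last observation carried forward method for all outcome measures". It covers every outcome and names two kinds of data, missing and incomplete. It does not define the second kind, state a minimum number of answered items, or say whether the value carried forward is an item answer or a scale total.

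Other parts of the protocol determine what the rule does:

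- Outcomes: "Assessments will take place at baseline and 12 weeks after randomisation". No intermediate visit could supply a later value.
- Primary Measures, Fatigue: the MFIS has "21 items that assess the impact of fatigue on cognitive, physical, and psychosocial functioning" and the PFS has "16 items that mostly measure the experience of fatigue". Each is described by its total score, 0 to 84 and 0 to 80.
- Efficacy Analyses: the primary outcome is analysed "using the parametric student-t test for comparing mean change between the two intervention groups".
- Aims: the size and variance of the difference in change are to feed the sample size of the full trial.
- Outcomes, on carrying two fatigue scales: "so we will use both measures to determine which is most sensitive to any changes caused by the ReFresh program".
- Data security: most assessments are completed online, but "participants will be offered hard copy survey and consent forms to be posted to them". The protocol does not say whether the online survey forces an answer to each item.

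**The concern.** This point is about people who do return the week-12 survey, not about dropouts. A form with 20 of 21 MFIS items, or 15 of 16 PFS items, is incomplete in the ordinary sense of the word. If the rule acts on the total, the week-12 score is discarded and baseline takes its place, although nearly all the follow-up information was observed.

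The pilot exists to supply the mean difference in change and its variance, and to choose between the two fatigue scales. Replacing observed changes by zero pulls the mean change and its SD downwards, and could do so to different degrees on scales of different length. A better method for dropouts would not cure this, because a partly completed form would still be classed as data to be imputed.

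**Working it through.** **Inputs from the protocol.** MFIS 21 items, PFS 16 items, PDQ-39 39 items. Two assessment times. Analysis on mean change. Sample size 20 + 20 = 40, which is arithmetic only. The protocol gives no missing-data or item-skip rate, so there is no figure of its own to reproduce on this point.

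**Assumed input.** A per-item skip rate q, independent between items and equal on both scales, varied from 0.5% to 2%.

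**Step 1: value carried.** With baseline and week 12 only, the last earlier observation is baseline. Imputed change = baseline − baseline = 0.

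**Step 2: total-score reading.** P(at least one item skipped) = 1 − (1 − q)^k, where k is the number of items. The share of the true mean change that is kept is (1 − q)^k. At q = 1%:

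- MFIS: 1 − 0.99^21 = 0.190
- PFS: 1 − 0.99^16 = 0.149

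| q | MFIS overwritten | PFS overwritten | People of 40, MFIS / PFS | Mean change kept, MFIS / PFS |
|---|---|---|---|---|
| 0.5% | 10.0% | 7.7% | 4.0 / 3.1 | 90% / 92% |
| 1% | 19.0% | 14.9% | 7.6 / 5.9 | 81% / 85% |
| 2% | 34.6% | 27.6% | 13.8 / 11.0 | 65% / 72% |

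The counts assume that all 40 return a form. For the PDQ-39, treated as one 39-item form, the same formula gives 17.8%, 32.4% and 54.5%.

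**Step 3: item-level reading.** Only the skipped item takes its baseline answer. If change is spread evenly over items, one skip loses 1/21 = 4.8% of that person's MFIS change or 1/16 = 6.3% of the PFS change. The expected share kept is about 1 − q on both scales (99% at q = 1%, 98% at q = 2%), whatever the scale length.

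**Step 4: clustered skips, total-score reading.** Keep the overall rate at 1%, but let 5% of respondents each skip 20% of items (an illustration, not a protocol figure):

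- MFIS: 0.05 × (1 − 0.8^21) = 5.0%
- PFS: 0.05 × (1 − 0.8^16) = 4.9%

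The overwritten share falls from 19% and 15% to about 5%, and the difference between the scales almost disappears.

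**Step 5: effect on the definitive sample size, total-score reading, q = 1%, independent skips.** The direction depends on how the pilot is used.

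- *Pilot SD with a target difference from elsewhere.* With mean change near 0, the SD is multiplied by √(1 − p), where p is the overwritten share: √0.81 = 0.90 (MFIS) and √0.85 = 0.92 (PFS). Sample size goes with SD², so it is about 19% and 15% too small.
- *Pilot's own standardised effect.* Let c be the share kept, d = 0.5 the assumed true standardised difference, and let the control group have mean change 0. The treated-arm variance is c(1 + d²) − (cd)² and the control variance is c. The apparent effect is cd divided by the root of their average: 0.445 (MFIS) and 0.457 (PFS). At two-sided 5% and 90% power this gives 107 and 101 per arm, against 85 with no loss. 107/85 = 1.26 and 101/85 = 1.19, so the trial would be about 26% and 19% too large.

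**The case against.** The strongest reply is that the sentence does not say what a critic might make it say. Covering all outcome measures tells us which outcomes are included, not whether the rule works on items or totals. Missing and incomplete may be a loose pair, or incomplete may mean a survey abandoned part-way. Under item-level use almost nothing is lost. Item scoring is also commonly left to an analysis plan, and exposure is unknown: most forms are online, the online survey may force answers, and paper is offered for accessibility needs.

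Much of this stands. Three stronger readings are tempting, and the protocol supports none of them.

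- *That the protocol prescribes replacing the whole score after one skipped item.* It permits this but does not state it.
- *That the MFIS is materially disadvantaged because it is longer.* That needs the total-score reading, independent skips and equal skip rates. Even then, at q = 1% the apparent effects differ by 0.457 − 0.445 = 0.012, against a standard error of about √(2/20) = 0.32 for one standardised difference with 20 per arm. With clustered skips the gap almost vanishes.
- *That the definitive trial would be too small.* That holds only for an SD paired with an outside target. The first aim refers to both size and variance, and using both makes the trial too large.

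What does not stand is the claim that this is only unstated detail. The protocol fixes a treatment for incomplete data on every measure, and an analysis plan that prorated partly completed scales would depart from it.

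**Conclusion.** The point holds in conditional form. The protocol applies carry-forward to incomplete data without defining the term or the level, and the carried value can only be baseline. A reasonable analyst could follow the sentence and overwrite nearly complete primary-outcome responses with no change.

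The size depends on the reading. At total-score level, with independent skips at 0.5% to 2% per item, about 10% to 35% of MFIS and 8% to 28% of PFS responses would be overwritten, and mean change would shrink by the same share. With clustered skips the loss is far smaller. At item level it is about 1/21 or 1/16 of one person's change per skipped item. The skip rates, their independence and their equality across scales are assumptions, since the protocol gives none of them. The effect on the definitive sample size can go either way, and any tilt between the two scales is modest.

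The change should be made: it is cheap, and it protects observed data in a pilot whose first aim is to estimate change and its variance.

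**What to change.** Remove incomplete data from the carry-forward sentence in Efficacy Analyses. State that a partly completed scale is scored from the answered week-12 items, by the instrument's own missing-item rule or, where there is none, by prorating when at least a pre-set share of items is answered. Half is one example; the protocol gives no threshold, so the team should choose it before seeing data. Only forms below that minimum count as missing.

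The cost is one sentence and a few lines of scoring syntax. The small downside is that prorating assumes the skipped items resemble the answered ones.
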